	
majority of patients with sepsis who qualify for this study to be receiving VV-ECMO.
 
Study population
 
The study population will include eight critically ill adult patients (<math>\geq 18</math> years of age) receiving ECMO support in the medical or surgical intensive care units at Hartford Hospital. Patients with documented or presumed infection are eligible. Any patient with infection will be treated with standard antibiotics by the attending provider. To ensure representation of patients across the renal function spectrum to be included in the study, half of the enrolled patients will have a creatinine clearance <math>\geq 60</math> mL/min at screening and half will have a value between 15 and 59 mL/min.
 
Inclusion Criteria: Patients eligible to participate in the study must meet all of the following criteria prior to any study-related procedure:
 
 
• Age 18 years or older;
 
• On support with VV- or VA-ECMO;
 
• Documented infection or presumed infection as confirmed by the presence of at least one of the following criteria within the past 72 hours: 
 
◦ Documented fever (oral, rectal, tympanic, or core temperature <math>> 38.5^{\circ}</math> C)
 
◦ Hypothermia (oral, rectal, tympanic, or core temperature <math>< 35.0^{\circ}</math> C)
 
◦ An elevated white blood cell (WBC) count <math>\geq 12,000</math> cells/mm<math>^3</math>
 
 
 
 
Exclusion Criteria: Patients will be considered ineligible if they meet any of the following criteria:
 
 
• If female, currently pregnant or breast feeding;
 
• History of any moderate or severe hypersensitivity or allergic reaction to any <math>\beta</math>-lactam agent (a history of mild rash to a <math>\beta</math>-lactam followed by uneventful re-exposure is not a contraindication);
 
• Severe renal dysfunction defined as a creatinine clearance <math>< 15</math> mL/min (calculated by the Cockcroft-Gault equation using actual body weight) or requirement for continuous renal replacement therapy or hemodialysis;
 
• Hemoglobin less than 8 mg/dL at baseline;
 
• Use of probenecid or imipenem within 3 days before study drug infusion;
 
• Current use of valproic acid or anticipated use during study enrollment.
 
• Acute liver injury, defined as aspartate aminotransferase (AST) or alanine aminotransferase (ALT) <math>> 5</math> times the upper limit of normal, or AST or ALT <math>> 3</math> times the upper limit of normal with an associated total bilirubin <math>> 2</math> times upper limit of normal;
 
• Any rapidly-progressing disease or immediately life-threatening illness (defined as imminent death within 48 hours in the opinion of the investigator);
 
• Any condition or circumstance that, in the opinion of the investigator, would compromise the safety of the patient or the quality of study data;
 
 
Planned or prior participation in any other interventional drug study within 30 days.
 
Study Procedures
 
Screening/Baseline
 
Screening/Baseline assessments and procedures must be completed within 24 hours before the start of the study drug infusion. Potential subjects who do not meet enrollment criteria may, as appropriate, repeat the screening assessments once at a later time for possible enrollment into the study. Local laboratory results will be used to determine subject eligibility for study enrollment. Any protocol-required eligibility laboratory evaluations already done as part of the patient's regular medical care within 24 hours before the start of the study drug infusion on Study Day 1 do not

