2.9 Adverse Experience Reporting	
Safety and Adverse Event Monitoring
 
Participants will be monitored for any sign or symptom of adverse events (AE) throughout the course of the study. Unanticipated, life-threatening or fatal adverse events will be reported to the IRB, the manufacturer, and the Food and Drug Administration according to federal guidelines. All adverse events requiring medical attention will be treated by the study physician and will be recorded by the investigator. For the purpose of this study, an adverse event will be defined as any pathologic or unintended change in the structure (signs), function (symptoms), or chemistry (laboratory values) of the body associated with the use of the study drug, whether or not considered drug related, and will be categorized as one of the following:
 
 
• MILD – present, but easily tolerated
 
• MODERATE – discomfort that interferes with usual activities
 
• SEVERE – incapacitating, inability to work or do usual activities
 
 
Relationship of the AE to the study medication (i.e., causality) will be evaluated according to the investigator's opinion, as one of the following:
 
 
• Concurrent condition – unrelated to study drug
 
• REMOTE adverse drug event – little or no temporal relationship to study drug
 
• POSSIBLE adverse drug event – temporal relationship to study drug
 
• PROBABLE adverse drug event – commonly associated with study drug
 
• DEFINITE adverse drug event – reappeared on re-challenge of study drug
 
 
All SAEs will be reported to the Institutional Review Board, sponsor, and the Food

	and Drug Administration according to Federal and local guidelines. A serious adverse event will be defined as any adverse event that results in death, is immediately life-threatening, requires or prolongs hospitalization, or is an important medical event that may jeopardize the participant or may require medical intervention to prevent one of the previously mentioned outcomes.
2.10 Itemized Study Budget	See Proposed Budget

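### The moderate and severe adverse-event grades depend on usual activities or work, already lost in ICU patients on ECMO, and no grade has a criterion that fits laboratory events

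*Combined protocol and SAP*

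**What the plan says.** Section 2.9 (Adverse Experience Reporting) requires each adverse event to be placed in one of three severity grades. The lowest is "MILD – present, but easily tolerated". The middle one is "MODERATE – discomfort that interferes with usual activities". The highest is "incapacitating, inability to work or do usual activities". The events to be graded are defined broadly: besides signs they cover changes in "function (symptoms), or chemistry (laboratory values) of the body". Causality is rated on a separate scale, and serious adverse events are defined separately by their outcome.

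Section 2.5 (Study population) describes the eight participants as "receiving ECMO support in the medical or surgical intensive care units at Hartford Hospital", and the inclusion criteria require each of them to be "On support with VV- or VA-ECMO".

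**The concern.** The scale assumes a person who, before the event, was working or going about daily life. None of these participants is in that position. If the anchor is absent before dosing, it cannot show how much an event added, and the grade may reflect the underlying illness or the assessor's habit instead of the event. Laboratory events raise a second problem that does not depend on the ECMO setting: a change in creatinine or transaminases has no natural reading in terms of discomfort, activity or work.

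At stake is whether two assessors would give the same event the same grade. For a non-serious event, section 2.9 asks for only two ratings, severity and causality, and causality rests on the investigator's opinion. If the severity grade is not reproducible, little structured information is left about such events.

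**Working it through.** The plan states no figure on this point and no calculation applies. The check sets the grade definitions beside the population, the event definition and the uses of the grade.

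1. **What is graded.** Section 2.9 grades events, not patients. An event is a change, so incapacity already present before dosing is not itself an event.

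2. **State before the first dose.** Section 2.2 describes ECMO as support for heart or respiratory failure after conventional therapy has failed. Section 2.5 places every participant on ECMO in an intensive care unit, lets a representative or relative consent, and has ventilator support recorded. The documents do not say outright that participants cannot work or carry on daily life. That is an inference, but it follows closely from this description.

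3. **Each grade against that state.**

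| Grade | Anchor | Uses activities or work? | Laboratory criterion? |
|---|---|---|---|
| Mild | tolerability | no | none |
| Moderate | discomfort plus interference with activities | activities | none |
| Severe | incapacity; loss of work or activities | both | none |

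   Activities appear in 2 of 3 grades, work in 1 of 3, and a laboratory criterion in 0 of 3.

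4. **The moderate/severe boundary.** Take two hypothetical events in one participant, one needing a small adjustment of care and one needing an urgent response. Activities and work are absent before and after both, so the wording "discomfort that interferes with usual activities" and the wording for severe give no basis for ranking them. What remains is discomfort against incapacity. Discomfort depends largely on self-report, which will be limited in some of these patients. Incapacity is hard to attribute to an event in someone already incapacitated.

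5. **Laboratory events.** An asymptomatic shift can be called easily tolerated, but that is as true of a large shift as of a small one. The only criterion that could be applied does not grade the change.

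6. **Is a substitute given elsewhere?** No. The laboratory limits in section 2.5 serve eligibility and the renal-function split of enrolment. Sections 2.5, 2.7 and 2.9 contain no grading thresholds, no intervention-based criteria, no baseline reference for severity and no alternative scale.

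7. **What depends on the grade?** The single objective (section 2.1) is pharmacokinetic. Section 2.7 contains no analysis by severity. No stopping or reporting rule in the documents refers to the grade.

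**The case against.** The strongest reply is that the grade has little work to do here. Serious events are identified by outcome, causality has its own scale, life-threatening or fatal events have their own reporting sentence, and no analysis uses severity. All of this stands, and it limits the consequence. It does not make the scale usable: the protocol still requires the grade for every event, and seriousness does not rank non-serious events.

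A reader might also infer something stronger: that all eight participants meet the severe definition at baseline, that every event would then be graded severe, and that the safety results could not be interpreted. The documents do not support this. A participant without an event receives no grade. Mild has its own criterion, so a minor event can still be called mild. Incapacitating can be read as a property of the event. No severity-based safety summary is planned that could be spoiled, and clinical and laboratory data before and after dosing remain available for describing events.

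Nor should section 2.2 be read as declaring a safety gap. It reports an absence of data on relebactam disposition in ECMO patients, which is a pharmacokinetic statement about an approved product.

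Finally, grading by change in treatment or support may also follow the underlying illness, since support can change for other reasons, and an urgent-intervention grade comes close to the seriousness definition. Both points are fair. They are why the revised wording should tie the change to the event and keep severity apart from seriousness.

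**Conclusion.** The point holds in a limited form. As written, the moderate/severe boundary and the grades of laboratory events cannot be assigned reliably. The first part rests on the inference that ICU patients on ECMO have lost work and usual activities before dosing. The second part needs no such inference.

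The documents give no expected number or type of adverse events, so the share of grades affected cannot be calculated. The mild criterion, serious-event reporting and the pharmacokinetic results are unaffected. This is an inexpensive improvement to a required data item, and the study's main result does not depend on it.

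**What to change.** In section 2.9 and on the case report form, define the grades by observable change from the patient's own pre-dose state. For example, the event leads to no change, a change, or an urgent change in treatment or support, where the change is attributable to the event. Grade laboratory events by prespecified amounts of change from the baseline value. State that severity and seriousness are separate judgements, and leave the existing seriousness definition as it is.

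Most of the data needed are already collected. Vital signs, FiO2, ventilator support and the blood panel are recorded at screening and on Day 2, and concomitant medications on both study days. Two gaps in section 2.5 need a decision. ECMO settings are listed at screening but not on Day 2, so a change in ECMO support would not be captured by the listed assessments. Urinalysis is listed on Day 2 but not at screening, so it has no protocol baseline to grade against.

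The cost is a wording and form edit, including agreement on the laboratory thresholds, with no additional patients. The downside is that grades become less directly comparable with studies that use the activity-based scale.

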--	--

	
other intravenous medications will be co-administered with imipenem/cilastatin/relebactam.
 
Study Day 1
 
 
• Vital signs (temperature, heart rate, blood pressure, respiratory rate) will be recorded within 15 minutes prior to starting the study drug infusion.
 
• Participants will receive imipenem/cilastatin/relebactam as described above. Exact start and stop times will be recorded in military time.
 
• Identify, assess, and record any new adverse events or Serious Adverse Events (SAE)
 
• Concomitant medications will be recorded.
 
• Blood samples will be collected as described below.
 
 
Study Day 2
 
 
• Participants will receive imipenem/cilastatin/relebactam as described above. Exact start and stop times will be recorded in military time.
 
• Blood samples will be collected as described below.
 
• Concomitant medications will be recorded.
 
• Clinical Assessments:
 
• Perform a complete physical examination
 
• Record resting pulse, blood pressure, and respiratory rate; oxygen saturation (by pulse oximeter), including rate of supplemental oxygen (i.e., FiO2); ventilator support; and highest (or lowest if hypothermia) daily temperature (oral, rectal, tympanic, or core) measured
 
• Identify, assess, and record any new adverse events or SAE
 
• Laboratory Assessments:
 
• Collect the following labs within 24 hours after completion of last blood sample collection: serum creatinine, blood urea nitrogen, glucose, sodium, potassium, chloride, bicarbonate, albumin, total protein, complete blood count (CBC) with differential, total bilirubin, direct bilirubin, alkaline phosphate, alanine aminotransferase, aspartame aminotransferase, and urine analysis with microscopy.
 
 
Sample Collection
 
Blood samples (4 mL) will be collected in K2EDTA vacutainers before the first imipenem/cilastatin/relebactam dose (i.e., blank), and at 0.5 and 6 hours following the first dose, and then at 0, 0.5, 0.75, 1, 2, 4, 5, and 6 hours after the start of the final dose, when concentrations are expected to be at steady-state. All blood samples will be collected pre-oxygenator. Additionally, protein binding will be determined at the 0.5 hour time point of the final dose. The timing of all blood samples should be +/- 5 minutes of protocol defined time, except for the 0.5 hour (peak concentration), which can be +5 minutes the end of infusion and should be collected as close to the end of the infusion as possible.
 
Processing of clinical samples
 
Blood samples will be immediately stored on ice and centrifuged within 30 minutes of collection at 4° C and 1300 x g for 10 minutes to separate the plasma. Immediately after centrifugation, 1.0 mL of plasma from each sample will be transferred (using a 1.0 mL pipette) to a previously labeled cryovial containing 1.0 mL of plasma stabilizer (2-(N-morpholino) ethanesulfonic acid (MES)). A second 1.0 mL of plasma will be added to a second cryovial (labeled with stabilizer) to have a back-up sample. Thereafter, cryovials will be capped and inverted at least six times to mix the plasma with the stabilizer. The cryovials will be stored at -80° C until concentration determination. No more than 60 minutes should elapse between the blood draw and freezing of plasma sample.

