
	
package for R (Laboratory of Applied Pharmacokinetics and Bioinformatics, Los Angeles, CA) using either a one or two compartment model. Appropriate model selection will be based on visual inspection, observed versus predicted plots, and Akaike Information Criterion (AIC). The effect of specific body size descriptors (actual body weight, ideal body weight, body mass index, body surface area), calculated CrCL, and ECMO flow rate will be analyzed for correlation with pharmacokinetic parameters (i.e., CL and volume of distribution). By including a similar proportion of participants with creatinine clearance above and below 60 ml/min, a variable range of clearance values will be represented in the population analyses.
 
Pharmacodynamic Analysis
 
The free imipenem and relebactam concentration of each of the eight participants will be assessed for free time above the MIC (<math>fT > MIC</math>, applied for imipenem) and free area under the curve to MIC (<math>fAUC/MIC</math>, applied for relebactam) exposure using the imipenem susceptibility breakpoint of 2 <math>\mu</math>g/mL for Pseudomonas aeruginosa.
 
Sample Size
 
No target sample size is provided statistically as this will be a descriptive and exploratory study. Therefore, this study will enroll eight critically ill adult patients on ECMO support based primarily on empirical considerations and feasibility. This number is considered sufficient to meet the study objectives.

2.8 Specific Drug Supply Requirements	
Recarbrio® (Imipenem/cilastatin/relebactam) 1.25g vials (n=50 vials)

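### The SAE definition in section 2.9 has no disability criterion, so whether an anticipated, non-life-threatening disabling event counts as serious is left to judgment

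*Combined protocol and SAP*

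**What the plan says.** Section 2.9 (Adverse Experience Reporting) holds the only SAE definition in the document. An event is serious if it "results in death, is immediately life-threatening, requires or prolongs hospitalization, or is an important medical event that may jeopardize the participant", or if it "may require medical intervention to prevent one of the previously mentioned outcomes".

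Two sentences in the same section send events outside the site:

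- For serious events: "All SAEs will be reported to the Institutional Review Board, sponsor, and the Food" and Drug Administration, in line with federal and local guidelines.
- Separately, and without using the term SAE: "Unanticipated, life-threatening or fatal adverse events will be reported to the IRB, the manufacturer" and the FDA.

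Incapacity appears once in the section, as the top severity grade: "SEVERE – incapacitating, inability to work or do usual activities". No rule connects that grade to SAE status.

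On setting and timing, section 2.5 enrolls patients "receiving ECMO support in the medical or surgical intensive care units at Hartford Hospital". Its last scheduled assessments are those of Study Day 2, with laboratory tests "within 24 hours after completion of last blood sample collection".

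**The concern.** The definition reads as a closed list, and lasting harm is not on it. Outside an intensive care unit the hospitalization criterion would pick up many disabling events, because such events tend to bring a patient into hospital. Here every participant is already an inpatient on life support, so that criterion does less than usual. What is left for a non-fatal disabling event depends on judgment.

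At stake is the serious or non-serious label and the reporting that follows from it. SAE status triggers the only rule in section 2.9 that sends every serious event to the IRB, the sponsor and the FDA, whether or not it was anticipated. A new neurological or organ deficit could be found, since a complete physical examination and a chemistry panel are planned on Study Day 2. It could then be carried as non-serious in keeping with the protocol's own words.

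**Working it through.** There is no figure to reproduce. The document gives no power calculation ("No target sample size is provided statistically as this will be a descriptive and exploratory study"), and the point turns on wording. The check takes one kind of event through each criterion: an adverse event that leaves a disabling deficit, is not fatal, is not immediately life-threatening, and was anticipated.

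| Criterion in section 2.9 | Does it oblige serious classification? |
|---|---|
| Death | No, by construction. |
| Immediate threat to life | No, by construction. |
| Requires hospitalization | It does not discriminate: every participant is already in intensive care (section 2.5). |
| Prolongs hospitalization | Possibly. It needs a view of how long the stay would otherwise have been, and no assessment is scheduled after Study Day 2 and the closing laboratory tests. |
| Important medical event that may jeopardize the participant | Possibly, if the investigator elects to call it that. |
| Intervention to prevent a listed outcome | Not for disability as such. It reaches back only to death, threat to life and hospitalization. |

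No row obliges the event to be classed as serious. Two rows allow it, and both rest on judgment.

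Next, whether another part of the section closes the gap:

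1. *Severity grade.* The SEVERE grade mentions incapacity but carries no reporting consequence. It also separates poorly in patients on ECMO in intensive care, who cannot do usual activities to begin with.
2. *The separate reporting sentence.* It can be read in two ways. If unanticipated events are a category of their own, an unanticipated disabling event goes to the IRB, the manufacturer and the FDA, though not labeled as an SAE. If the word only qualifies the two categories after it, such an event is not covered. On either reading an anticipated, non-life-threatening disabling event falls outside.
3. *The reference to federal and local guidelines.* This governs how SAEs are reported. Which events enter that route is set by the protocol's own definition.

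Size of the exposure: 8 participants × 4 doses = 32 doses at the least, and 8 × 6 = 48 at the most. The document gives no rate for disabling events. An expectation of zero or one affected event is a judgment, not a calculated figure.

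**The case against.** The strongest reply is that the gap is one of discretion only. The limb on important medical events that may jeopardize the participant stands by itself and is not tied to the listed outcomes. On an ordinary reading, a lasting neurological or organ deficit fits it. An investigator who wished to class such an event as serious could do so. This stands. It rules out the stronger reading that each disabling event would be misclassified or would go unreported; the text supports only *could*.

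Second, a reader might infer that the hospitalization criterion is close to inoperative in all eight participants. The documents do not show that. Being an inpatient defeats *requires*, not *prolongs*. The background section describes ECMO as temporary, and nothing says that ECMO sets the length of the hospital stay. A new deficit could well lengthen it. What stands is narrower: the criterion is hard to apply with no scheduled look beyond Study Day 2.

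Third, a reader might infer that the safety result of the study would understate serious harm. That goes too far. The sole objective is pharmacokinetic, section 2.7 plans no SAE summary or formal safety analysis, and adverse events are collected on the case report form and graded. The harm would still be in the data; only its label and its onward reporting are in doubt.

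Finally, the federal and local guidelines are not in the document, so it cannot be excluded that they would call for reporting despite the shorter protocol list. That limits what can be said about reporting in practice. It does not change what the protocol's definition says.

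**Conclusion.** The omission is real, and nothing else in the document repairs it. An anticipated, non-fatal, non-life-threatening disabling event is serious under section 2.9 only if it is judged to prolong the stay or the investigator elects to call it an important medical event. Otherwise it could be recorded as non-serious and not sent as an SAE. Unanticipated events may still be reported under the separate sentence.

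The practical effect is small: at most a rare event among eight participants, with no bearing on the PK results. The change is still worth making, because the gap comes from a stated rule and closing it is nearly free.

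The conclusion assumes that the definition in section 2.9 is meant to be complete, as its wording suggests, and that no site procedure outside the document adds a disability criterion.

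**What to change.** In the SAE definition of section 2.9, insert *results in persistent or significant disability/incapacity* directly after the hospitalization criterion and before the important medical event clause. In that position it becomes an explicit criterion, and it is also one of the outcomes to which the intervention clause refers back.

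The cost is one phrase in the next protocol amendment and, at most, an occasional extra SAE report. No dose, sampling time, eligibility rule or analysis changes.

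The phrase will not remove all judgment. With no later visit scheduled, persistence will seldom be established within the study, so an event will usually have to qualify on significance, which the investigator still has to assess.
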